### **5.1.3 Subject Exclusion Criteria**

The subject must be excluded from participating in the trial if the subject:

1. Has inability to swallow oral medications or presence of a gastrointestinal disorder (e.g. malabsorption) deemed to jeopardize intestinal absorption of MK-8628.
2. Has persistent grade >1 clinically significant toxicities related to prior antineoplastic therapies (except for alopecia); stable sensory neuropathy ≤ grade 2 National Cancer Institute (NCI)-CTCAE v. 4.0 is accepted.
3. Has known primary CNS malignancy or symptomatic or untreated CNS metastases. Treated and stable CNS metastases are allowed.
4. Has a history of prior or concomitant malignancies (other than excised non-melanoma skin cancer or cured *in situ* cervical carcinoma) within 3 years of signing informed consent.
5. Has other serious illness or medical condition, such as active infection, unresolved bowel obstruction, psychiatric disorders, or cerebrovascular accident (within 1 year of study entry).
6. Has known history of Human Immunodeficiency Virus (HIV) (HIV 1/2 antibodies).
7. Has known active Hepatitis B (e.g. hepatitis B surface antigen [HBsAg] reactive) or Hepatitis C (e.g. hepatitis C viral [HCV] RNA [qualitative] is detected).
8. Has any of the following cardiac-related conditions:
  - a. Congestive heart failure or angina pectoris (except if medically controlled)
  - b. Previous history of myocardial infarction (within 1 year of study entry)

- c. Uncontrolled hypertension (defined as systolic blood pressure > 140 mmHg, and/or diastolic blood pressure > 90 mmHg, and not adequately managed by anti-hypertensive medication)
  - d. Uncontrolled arrhythmias
9. Has participated in another clinical trial or treatment with any investigational drug (excluding anticancer treatments) within 30 days prior to study entry.
  10. Has other concomitant anticancer treatment, except the use of anti-androgens in CRPC subjects.
  11. Has concomitant therapy with strong CYP3A4 inhibitors or inducers.
  12. Is currently using therapeutic anticoagulation (e.g. warfarin, heparin, etc.) (Must be stopped at least 7 days prior to the first dose of MK-8628). Low-dose low molecular weight heparin (LMWH) is permitted.
  13. Has a history or current evidence of any condition, therapy, lab abnormality or other circumstance that might expose the subject to risk by participating in the trial, confound the results of the trial, or interfere with the subject's participation for the full duration of the trial.
  14. Is pregnant or breast-feeding.

## 5.2 Trial Treatment(s)

The treatments to be used in this trial are outlined below in [Table 2](#) and [Table 3](#).

Table 2: Trial Treatments – Part A: Dose Escalation

Drug	Dose/Potency	Dose Frequency	Route of Administration	Regimen/Treatment Period
MK-8628	20 mg	BID	Oral	Continuous / 21 days per cycle
MK-8628	30 mg	BID	Oral	Continuous / 21 days per cycle
MK-8628	40 mg	BID	Oral	Continuous / 21 days per cycle

Table 3: Trial Treatments – Part B: NMC Cohort

Drug	Dose/Potency	Dose Frequency	Route of Administration	Regimen/Treatment Period
MK-8628	10 mg	BID	Oral	Continuous / 21 days per cycle
MK-8628	20 mg	BID	Oral	Continuous / 21 days per cycle
MK-8628	30 mg	BID	Oral	Continuous / 21 days per cycle
MK-8628	40 mg	BID	Oral	Continuous / 21 days per cycle

The first dose of trial treatment will be administered at the trial site in the morning of the Cycle 1 Day 1 Visit, and then again in the evening. Subsequent dosing will be performed twice daily either at the trial site on scheduled Visit days, or by the subject (i.e., unsupervised at his/her home), at approximately the same times each day.

All supplies indicated in [Table 2](#) and [Table 3](#) above will be provided centrally by the Sponsor or locally by the trial site, subsidiary or designee, depending on local country operational or regulatory requirements.

For any commercially available product that is provided by the trial site, subsidiary or designee every attempt will be made to source these supplies from a single lot/batch number. The trial site is responsible for recording the lot number, manufacturer, and expiry date for any locally purchased product as per local guidelines unless otherwise instructed by the Sponsor.

The investigator shall take responsibility for and shall take all steps to maintain appropriate records and ensure appropriate supply, storage, handling, distribution and usage of trial treatments in accordance with the protocol and any applicable laws and regulations.

### **5.2.1 Dose Selection/Modification**

#### **5.2.1.1 Dose Selection (Preparation)**

The rationale for selection of doses to be used in this trial is provided in Section 4.0 – Background & Rationale. There are no specific calculations or evaluations required to be performed in order to administer the proper dose to each subject.

#### **5.2.1.2 Dose Escalation (Part A)**

A twice daily (BID) dose escalation will be performed using a 6+8 two-stage design with continuous DLT rate monitoring via a modified toxicity probability index (mTPI) (Ji design), targeting a maximum 25% DLT rate [1].

Starting from 20 mg BID, up to three planned dose levels may be evaluated: 20 mg BID, 30 mg BID 40 mg BID (all continuous daily). See [Table 4](#) and [Table 5](#) for the dose escalation scheme.

Table 4: Dose Escalation Scheme

Dose Level (DL)	MK-8628 (mg/dose)	Outcome (#DLT/#Subjects)* / Actions to be taken
	BID Regimen (continuous)	
DL 1	20	At each DL: - Escalate/de-escalate per DLT rate observed using mTPI Table ( Table 5 )
DL 2	30	
DL 3	40	

\* Evaluated during the first 21 days of treatment

Table 5: Modified Toxicity Probability Interval (mTPI) Design

Number of toxicities	Number of subjects treated at current dose								
	6	7	8	9	10	11	12	13	14
0	E	E	E	E	E	E	E	E	E
1	S	E	E	E	E	E	E	E	E
2	S	S	S	S	S	S	S	S	E
3	D	S	S	S	S	S	S	S	S
4	DU	DU	DU	D	S	S	S	S	S
5	DU	DU	DU	DU	DU	D	S	S	S
6	DU	DU	DU	DU	DU	DU	DU	DU	D
7		DU	DU	DU	DU	DU	DU	DU	DU
8			DU	DU	DU	DU	DU	DU	DU
9				DU	DU	DU	DU	DU	DU
10					DU	DU	DU	DU	DU
11						DU	DU	DU	DU
12							DU	DU	DU
13								DU	DU
14									DU

E = Escalate to the next higher dose  
S = Stay at the current dose  
D = De-escalate to the next lower dose  
DU = The current dose is unacceptably toxic  
Target toxicity rate = 25%

Subjects may be enrolled continuously, such that the number of subjects who are enrolled but are not yet fully evaluable for DLT assessment may not exceed the number of remaining subjects who are at risk of developing a DLT before the dose would be considered unacceptably toxic. If 0 out of the first 6 subjects in a given dose level develop a DLT, then the dose can escalate to the next level without further expansion. If 3 subjects out of the first 6 subjects develop a DLT, the dose will be de-escalated to the next lower dose level. If  $\geq 4$  out of the first 6 subjects develop a DLT, this indicates an unacceptable toxicity. If 1 to 2 out of the first 6 subjects of a given dose level develop a DLT, expand the current dose level according to [Table 5](#) by continuing enrollment as follows. As stated above, the number of subjects who are enrolled at that dose but are not yet fully evaluable for DLT assessment may not exceed the number of remaining subjects who are at risk of developing a DLT before the dose would be considered unacceptably toxic (denoted as DU in [Table 5](#)). For example, if 2/7 subjects have experienced a DLT at a given dose level, no more than an additional 3 subjects should be enrolled at this dose level until additional DLT data are available. This is because this dose level would be considered unacceptably toxic if all 3 of the additional subjects experience a DLT (i.e., 5/10 subjects with DLT in [Table 5](#)). To find out how many more subjects can be enrolled, one can count steps in diagonal direction (down and to the right) from the cell (7 subjects, 2 toxicities) to the first cell marked DU.

De-escalation (D) or unacceptable (DU) at the starting dose level (DL1) indicates stopping of the trial. Escalation (E) at the highest dose level (DL3) indicates staying at that level. Note that while 25% has been the target toxicity rate used to generate the guidelines in [Table 5](#), the observed rate of subjects with DLT at the RP2D may be slightly above or below 25%.

Subjects not evaluable for DLT (i.e. receiving less than 85% of the intended cumulative dose in Cycle 1 for any reason other than toxicity; <18 days of treatment) and who do not experience DLT will be replaced.

Subjects will receive MK-8628 at the DL they were assigned at entry throughout the study, or at a reduced dose according to toxicity encountered. Subjects will undergo a dose and/or schedule modification in the event of toxicity (see Section 5.2.1.6 and 5.6.1.1).

### 5.2.1.3 NMC Cohort (Part B)

An additional cohort of NMC subjects will be treated in a parallel study. This study will only include NMC subjects. Priority for treatment allocation will be to enroll into Part A of the study (Dose Escalation). If there are no slots available in Part A at the time the NMC subject is identified, the subject will be enrolled and allocated to treatment in Part B (NMC Cohort).

As in Part A, dose administration will be continuous for 21 consecutive days per cycle (21-day cycles). NMC subjects enrolled in Part B will be treated at one dose level below the current dose level from the dose escalation study in Part A. Therefore, a starting dose of 10 mg BID will be administered, and up to four dose levels will be evaluated: 10, 20, 30 and 40 mg BID, continuous, 21-day cycles. Once the RP2D is established, newly enrolled NMC subjects in Part B may be treated at the RP2D. See [Table 6](#) for the dosing scheme for the NMC Cohort study.

Table 6: Dosing Scheme for NMC Cohort

Dose Level (DL)	Current Dose Level from Part A: Dose Escalation	Dose to Treat in Part B: NMC Cohort
DL1	20 mg BID, continuous	10 mg BID, continuous
DL2	30 mg BID, continuous	20 mg BID, continuous
DL3	40 mg BID, continuous	30 mg BID, continuous
RP2D*	N/A	20, 30 or 40 mg BID, continuous

\*Once the RP2D is established, newly enrolled NMC subjects in Part B may be treated at the RP2D.

Subjects will receive MK-8628 at the DL they were assigned at entry throughout the study, or at a reduced dose according to toxicity encountered. Subjects will undergo a dose and/or schedule modification in the event of toxicity (see Section 5.2.1.6 and 5.6.1.1).

### 5.2.1.4 Dose Limiting Toxicity

For the dose escalation part of this study (Part A), a DLT is defined as any of the following toxicities occurring during the first cycle of treatment (21 days) for each dose level. See Section 5.9 for rules on replacement of subjects in the DLT period.

The occurrence of any of the following toxicities during Cycle 1, **if assessed by the investigator to be possibly, probably or definitely related to MK-8628**, will be considered a DLT:

Hematologic toxicity

- Grade 4 hematologic toxicity lasting  $\geq 7$  days, except thrombocytopenia
  - Grade 4 thrombocytopenia of any duration
  - Grade 3 thrombocytopenia is a DLT if associated with bleeding
- Febrile neutropenia Grade 3 or Grade 4

Non-hematologic toxicity

- Grade 4 non-hematologic toxicity (not laboratory)
- Grade 3 non-hematologic toxicity (not laboratory) lasting  $> 3$  days despite optimal supportive care. Grade 3 nausea, vomiting or diarrhea will be considered a DLT if lasting more than 3 days despite optimal supportive care.
- Any Grade 3 or 4 non-hematologic laboratory abnormality, if:
  - medical intervention is required, or
  - the abnormality leads to hospitalization, or
  - the abnormality persists for  $> 1$  week
- Any of the following liver test abnormalities are observed (see also Section 12.7):
  - ALT or AST  $> 8X$  ULN
  - ALT or AST  $> 5X$  ULN for more than 2 weeks
  - ALT or AST  $> 3X$  ULN **AND** (total bilirubin  $> 2X$  ULN **OR** INR  $> 1.5$ )
  - ALT or AST  $> 3X$  ULN with the appearance of fatigue, nausea, vomiting, right upper quadrant pain or tenderness, fever, rash and/or eosinophilia ( $> 5\%$ ), unless the investigator assesses the rash or fatigue to be related to MK-8628 and not related to liver impairment, with Sponsor's agreement

Other

- Any drug-related AE which caused the subject to discontinue treatment during Cycle 1
- Any study drug-related toxicity resulting in a subject missing  $\geq 20\%$  of planned doses during Cycle 1.
- Any treatment-related toxicity which causes a greater than 2 week delay in initiation of Cycle 2.
- Grade 5 toxicity

DLTs must be reported within 24 hours to the Sponsor as Events of Clinical Interest (see Section 7.2.3.2). If the event also meets the criteria for seriousness, follow the reporting guidelines for Serious Adverse Events (SAEs) outlined in Section 7.2.3.1.

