Preliminary clinical activity has been observed at a range of dose levels, including objective responses at 40 mg QD (1 CR), 80 mg (complete response with incomplete blood count recovery [CRi]) and 160 mg (CR) in the AL cohort and at 80 mg QD (1 PR) and 120 mg (2 CR) in DLBCL subjects.

A total of 49 subjects had been treated in the expansion cohorts with non-continuous dosing at 80 mg QD, 14 days ON/7 days OFF: 16 acute myeloid leukemia (AML) post-myelodysplastic syndrome (MDS) subjects, 18 AML non-MDS related (i.e. de novo, secondary to chemotherapy or myeloproliferative disorder [MPD]) subjects, and 15 diffuse large B-cell lymphoma (DLBCL) subjects. The expansion cohort demonstrated that at 80 mg QD, 14 days ON/7 days OFF was reasonably well tolerated with no DLTs reported. However, one subject with AML had grade 3 asthenia, deemed not related by the investigator

after clarification (related to aspergilliosis), and one subject with AML had a dose reduction due to poor tolerance (asthenia, anorexia, dysgueusia G2).

In the dose expansion cohort, one PR has been reported to date in a DLBCL subject along with evidence of clinical activity not yet meeting standard response criteria in some ongoing subjects (decrease in bone marrow blasts in five AML subjects and decreased lymph node lesions in two DLBCL subjects)

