## **7.1.2 Clinical Procedures/Assessments**

### **7.1.2.1 Adverse Event (AE) Monitoring**

The investigator or qualified designee will assess each subject to evaluate for potential new or worsening AEs as specified in the Trial Flow Chart and more frequently if clinically indicated. Adverse experiences will be graded and recorded throughout the study and during the follow-up period according to NCI CTCAE Version 4.0. Toxicities will be characterized in terms including seriousness, causality, toxicity grading and action taken with regard to trial treatment.

Please refer to Section 7.2 for detailed information regarding the assessment and recording of AEs.

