\*Note: For further guidance on the monitoring, treatment and follow-up of any ECI related to potential drug-induced liver injury (DILI), please see Section 12.7.

5. For the purpose of this dose-finding study, any suspected DLT occurring during dose escalation will be considered as medically important and reported as an ECI. If the event also meets the criteria for seriousness, follow the reporting guidelines for Serious Adverse Events (SAEs) outlined in Section 7.2.3.1.

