### **7.2.4 Evaluating Adverse Events**

An investigator who is a qualified physician will evaluate all adverse events according to the NCI Common Terminology for Adverse Events (CTCAE), version 4.0. Any adverse event which changes CTCAE grade over the course of a given episode will have each change of grade recorded on the adverse event case report forms/worksheets.

All adverse events regardless of CTCAE grade must also be evaluated for seriousness.

Table 12: Evaluating Adverse Events

An investigator who is a qualified physician, will evaluate all adverse events as to:

V4.0 CTCAE Grading	Grade 1	Mild; asymptomatic or mild symptoms; clinical or diagnostic observations only; intervention not indicated.
	Grade 2	Moderate; minimal, local or noninvasive intervention indicated; limiting age-appropriate instrumental ADL.
	Grade 3	Severe or medically significant but not immediately life-threatening; hospitalization or prolongation of hospitalization indicated; disabling; limiting self-care ADL.
	Grade 4	Life threatening consequences; urgent intervention indicated.
	Grade 5	Death related to AE
Seriousness	A serious adverse event is any adverse event occurring at any dose or during any use of Sponsor's product that:	
	† Results in death ; or	
	† Is life threatening ; or places the subject, in the view of the investigator, at immediate risk of death from the event as it occurred (Note: This does not include an adverse event that, had it occurred in a more severe form, might have caused death.); or	
	† Results in a persistent or significant disability/incapacity (substantial disruption of one's ability to conduct normal life functions); or	
	† Results in or prolongs an existing inpatient hospitalization (hospitalization is defined as an inpatient admission, regardless of length of stay, even if the hospitalization is a precautionary measure for continued observation. (Note: Hospitalization for an elective procedure to treat a pre-existing condition that has not worsened is not a serious adverse event. A pre-existing condition is a clinical condition that is diagnosed prior to the use of a Merck product and is documented in the patient's medical history.); or	
	† Is a congenital anomaly/birth defect (in offspring of subject taking the product regardless of time to diagnosis); or	

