	Time Course	Did the AE follow in a reasonable temporal sequence from administration of the Sponsor's product? Is the time of onset of the AE compatible with a drug-induced effect (applies to trials with investigational medicinal product)?
	Likely Cause	Is the AE not reasonably explained by another etiology such as underlying disease, other drug(s)/vaccine(s), or other host or environmental factors

Relationship to Sponsor's Product (continued)	The following components are to be used to assess the relationship between the test drug and the AE: (continued)	
	Dechallenge	Was the Sponsor's product discontinued or dose/exposure/frequency reduced? If yes, did the AE resolve or improve? If yes, this is a positive dechallenge. If no, this is a negative dechallenge. (Note: This criterion is not applicable if: (1) the AE resulted in death or permanent disability; (2) the AE resolved/improved despite continuation of the Sponsor's product; or (3) the trial is a single-dose drug trial; or (4) Sponsor's product(s) is/are only used one time.)
	Rechallenge	Was the subject re-exposed to the Sponsor's product in this study? If yes, did the AE recur or worsen? If yes, this is a positive rechallenge. If no, this is a negative rechallenge. (Note: This criterion is not applicable if: (1) the initial AE resulted in death or permanent disability, or (2) the trial is a single-dose drug trial); or (3) Sponsor's product(s) is/are used only one time). NOTE: IF A RECHALLENGE IS PLANNED FOR AN ADVERSE EVENT WHICH WAS SERIOUS AND WHICH MAY HAVE BEEN CAUSED BY THE SPONSOR'S PRODUCT, OR IF REEXPOSURE TO THE SPONSOR'S PRODUCT POSES ADDITIONAL POTENTIAL SIGNIFICANT RISK TO THE SUBJECT, THEN THE RECHALLENGE MUST BE APPROVED IN ADVANCE BY THE SPONSOR CLINICAL DIRECTOR AS PER DOSE MODIFICATION GUIDELINES IN THE PROTOCOL.
	Consistency with Trial Treatment Profile	Is the clinical/pathological presentation of the AE consistent with previous knowledge regarding the Sponsor's product or drug class pharmacology or toxicology?
The assessment of relationship will be reported on the case report forms /worksheets by an investigator who is a qualified physician according to his/her best clinical judgment, including consideration of the above elements.		
Record one of the following	Use the following scale of criteria as guidance (not all criteria must be present to be indicative of a Sponsor's product relationship).	

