Yes, there is a reasonable possibility of Sponsor's product relationship.	There is evidence of exposure to the Sponsor's product. The temporal sequence of the AE onset relative to the administration of the Sponsor's product is reasonable. The AE is more likely explained by the Sponsor's product than by another cause.	
No, there is not a reasonable possibility of Sponsor's product relationship	Subject did not receive the Sponsor's product OR temporal sequence of the AE onset relative to administration of the Sponsor's product is not reasonable OR the AE is more likely explained by another cause than the Sponsor's product. (Also entered for a subject with overdose without an associated AE.)	

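### Does the Yes/No causality entry in Table 12 undermine the DLT count defined in Section 5.2.1.4?

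*Combined protocol and SAP*

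**What the plan says.** Section 5.2.1.4 lists the Cycle 1 toxicities that count and makes each a DLT "if assessed by the investigator to be possibly, probably or definitely related to MK-8628". Section 8.1 makes the proportion of subjects with at least one DLT in Cycle 1 the primary endpoint, and Section 5.2.1.5 says that rate drives dose selection.

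Adverse events in general follow a separate route. Section 7.1.2.1 states: "Toxicities will be characterized in terms including seriousness, causality, toxicity grading and action taken with regard to trial treatment". It adds: "Please refer to Section 7.2 for detailed information regarding the assessment and recording of AEs". In Section 7.2.4, Table 12 opens with "An investigator who is a qualified physician, will evaluate all adverse events as to", and on causality it says: "The assessment of relationship will be reported on the case report forms /worksheets by an investigator who is a qualified physician". The form takes one of two answers. Yes is labelled as a reasonable possibility of a relationship. No applies, among other cases joined by OR, when the temporal sequence is not reasonable "OR the AE is more likely explained by another cause than the" sponsor's product. The table calls these criteria guidance.

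Under Section 7.2.3.2, "any suspected DLT occurring during dose escalation will be considered as medically important and reported as an ECI". That section requires events of clinical interest to be reported whether or not they are related.

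**The concern.** The same Cycle 1 event meets two causality standards. The scale in Section 5.2.1.4 starts at possible. Table 12 weighs the product against other causes and asks which is likelier. An event judged possibly related, but more probably due to something else, passes the first and fits No on the second. The three-grade scale appears nowhere else, has no stated recording field and is not mapped to Yes/No. The event-of-clinical-interest report does not settle relatedness either, since it is made regardless of cause.

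Such calls do occur. Section 4.2.2 reports from the haematology study that "one subject with AML had grade 3 asthenia, deemed not related by the investigator" once another cause was put forward.

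If the DLT flag were programmed from the Yes/No entry, some events that count under Section 5.2.1.4 would drop out. The DLT rate would be biased downward and escalation would become more permissive. With 6 to 14 subjects per dose level, one event can matter.

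**Working it through.** **The plan's own DLT figures.** The 80% intervals in Table 13 are highest-posterior-density intervals of Beta(1 + x, 1 + n − x):

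- 1/6: Beta(2, 6) gives (0.040, 0.391).
- 2/6: Beta(3, 5) gives (0.146, 0.567).
- 3/14: Beta(4, 12) gives (0.102, 0.367).

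All 11 agree with the table to within 0.0005. Rows 0 to 6 of Table 5 (63 cells) are reproduced by the mTPI rule with target 0.25 and a Beta(1,1) prior. This assumes an equivalence half-width of 0.01 to 0.04 and a cutoff of 0.95 for DU, neither of which the plan states. The question is therefore what gets counted, not how the counts are handled.

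**The two texts side by side.**

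| | Section 5.2.1.4 | Table 12, Section 7.2.4 |
|---|---|---|
| Applies to | Listed Cycle 1 toxicities | All adverse events |
| Assessor | Investigator | Investigator (qualified physician) |
| Answer | Possible, probable or definite relation counts | Yes or No |
| Stated consequence | The event is a DLT | Relationship entry on the case report form |
| Used by | Sections 8.1, 8.4.1, 8.5.2 and 8.6.2, through the term DLT | Relationship of adverse events in Section 8.4.1 |

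None of the analysis sections makes DLT status depend on Table 12. The looser terms under the Other heading of the DLT list (drug-related and the like) sit beneath the same lead-in and take their threshold from it.

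**Sensitivity to one event, from Table 5.** Take x from 1 up to the first DU cell at each n, and compare the action at x with the action at x − 1.

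| n | 6 | 7 | 8 | 9 | 10 | 11 | 12 | 13 | 14 | Total |
|---|---|---|---|---|---|---|---|---|---|---|
| Cells | 4 | 4 | 4 | 5 | 5 | 6 | 6 | 6 | 7 | 47 |
| Action changes | 3 | 2 | 2 | 3 | 2 | 3 | 2 | 2 | 3 | 22 |

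The 22 changes are 9 S-to-E, 4 D-to-S, 4 DU-to-D and 5 DU-to-S. Section 5.2.1.2 makes some of them immaterial. At DL1, D and DU both stop the trial, so 22 − 4 = 18 remain. At DL3, E means staying, so 22 − 9 = 13 remain. All 22 apply only at DL2.

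For the first six subjects at a true rate of 0.25, P(1) = 6 × 0.25 × 0.75⁵ = 0.356, P(3) = 20 × 0.25³ × 0.75³ = 0.132 and P(4) = 15 × 0.25⁴ × 0.75² = 0.033. The probability of landing on a count where one event fewer changes the consequence is:

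- DL1: P(1) + P(3) = 0.488
- DL2: P(1) + P(3) + P(4) = 0.521
- DL3: P(3) + P(4) = 0.165

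**If the flag were taken from Yes/No.** Let f be the share of true DLTs recorded as No. The documents do not give f, so the values here are assumptions. The counted rate is 0.25 × (1 − f), and P(0 of 6) is (1 − that rate)⁶:

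- f = 0: 0.75⁶ = 0.178
- f = 0.2: 0.80⁶ = 0.262
- f = 0.5: 0.875⁶ = 0.449

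When Section 5.2.1.4 is followed, f has no bearing on the count.

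**The case for a change.** The best argument for a change is that the primary endpoint steers escalation, its source field is not named, and one sentence would name it. The flag can also affect the denominator: under Section 8.5.2 a subject below 85% of the planned dose is DLT-evaluable only if a DLT occurred, so a missed flag could remove that subject from both counts. The event-of-clinical-interest report, being blind to cause, brings the event to the sponsor without classifying it.

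The wording gap stands, and so does the point that reporting is not classification. The harm, however, depends on someone replacing an explicit endpoint definition with a general adverse event field, and nothing in the plan directs that. The denominator effect rests on the same step. The proposed sentence would mostly repeat what Section 5.2.1.4 already says.

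The zone of conflict is also narrow. A reasonable possibility ordinarily covers a possible relation, and Table 12 leaves the answer to clinical judgement, so many such events would be entered as Yes. Those entered as No would still reach the sponsor as suspected DLTs, which makes silent under-counting less plausible. The asthenia example comes from another study and gives no sign that two scales conflicted there.

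The cell counts are correct but unweighted, and the full 22 applies at one dose level only. Any design of this size reacts to a single event.

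**Conclusion.** No change is needed. Sections 5.2.1.4 and 7.2.4 word causality differently and do not refer to each other, but the DLT definition is complete in itself and the analysis sections rely on it. The missing link is a detail that an analyst fills by taking DLT status from the investigator's assessment under Section 5.2.1.4. On that assumption the effect on the DLT rate, on Table 5 decisions and on the DLT-evaluable population is zero. The remaining effect is presentational: a counted DLT might be listed as not related among the adverse events, which a footnote in the report can explain. The documents give no basis for estimating how many events would fall in the gap, so the one-event sensitivity (22, 18 or 13 of 47 cells, depending on dose level) is not a measure of expected bias.
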